7.2 Study Population

Prospective approval of protocol deviations to recruitment and enrollment criteria, also known as protocol waivers or exemptions, are not permitted.

7.2.1 Inclusion Criteria (Part A and Part B)

Patients are eligible to be included in this study only if all of the following criteria apply:

1. Patients aged 18 years or older or above minimum legal age to attend a clinical study on the day written informed consent is given.
2. **In Part A & A-2:** Patients with any previously treated solid tumor-type other than hepatocellular carcinoma or intrahepatic cholangiocarcinoma, confirmed by available pathology records and/or current biopsy, that is advanced (non-resectable or metastatic), or recurrent and progressing since last anti-tumor therapy, and for which no alternative, standard therapy exists.

In Part B (all cohorts):

- Cohorts B1 and B7:
 - Patients with locally advanced or metastatic, non-resectable NSCLC and documented PD-L1 expression on $\geq 50\%$ of tumor cells[#] (Cohort B1), or documented PD-L1 expression on $\geq 1\%-49\%$ of tumor cells[#] (Cohort B7)
 - Cohort B1 and B7 will be conducted in the US, Spain, UK, the Netherlands, Germany, and Taiwan. Patients must have received at least 1, and a maximum of 3, previous lines of therapy, including at least 1 previous line containing a PD-(L)1 checkpoint inhibitor. **For patients enrolled to Cohorts B1 and B7 in Germany, they must have received both an anti-PD-(L)1 therapy and a platinum-based chemotherapy (i.e., at least 2 prior lines of treatment) to be eligible for study entry.**
 - Patients must have disease that is resistant (i.e., primary resistant[&]) or refractory (i.e., secondary resistant[&]) to anti-PD-(L)1 therapy as defined by:
 - a) Has received at least 2 doses of an approved anti-PD-(L)1 monoclonal antibody.
 - b) Has demonstrated progressive disease after anti-PD-(L)1 therapy as defined by RECIST 1.1, which was subsequently confirmed by a second assessment no less than 4 weeks from the date of the first documented progressive disease to rule out pseudo-progression, if the latter could not be excluded by the investigator based on the initial imaging demonstrating disease progression.

[#] Prospective testing is not done for Cohort B1 and B7, i.e., inclusion relies on documented previous testing leading to initiation of anti-PD-(L)1 therapy.

[&] Primary vs. secondary resistance will be determined based on documented progression of patients following less than or at least 24 weeks on previous anti-PD-(L)1 therapy.

- Cohort B2:

- Patients with locally advanced or metastatic, non-resectable HPV-associated (i.e., HPV+ tumor) SCC of the anus, cervix, vulva, vagina, penis or oropharynx with documented PD-L1 expression on at least 1% of tumor and/or immune cells in the TME, as detected by a locally-assayed, FDA-cleared PD-L1 test or any PD-L1 test approved for use by local competent authority
- Cohort B2 will be conducted in the US, Spain, UK, the Netherlands, Germany, and Taiwan. For Cohort B2, disease progression must have been documented following a first-line standard-of-care anti-PD-1 monotherapy, anti-PD-1/chemotherapy or chemotherapy regimen or 2 previous lines of therapy including one line of anti-PD-1 checkpoint inhibitor therapy and one line of chemotherapy. Patients must:
 - a) Either have documented previous testing results indicating HPV positivity for the current tumor or, in absence of a positive previous HPV test result, the current tumor must be tested positive for HPV applying the local standard testing approach.
 - b) Have demonstrated progressive disease after standard first-line, or first- and second-line therapy, as defined by RECIST 1.1, or in the view of the Investigator be ineligible or unwilling to be treated with standard first- or second-line therapy.

NOTE: A maximum of 10 patients with oropharyngeal SCC and a minimum of 15 patients with cervical SCC and 15 patients with anal SCC, respectively, will be enrolled within the total of 40 patients in this cohort.

- Cohort B3:

- Patients with locally advanced or metastatic, non-resectable NSCLC and documented PD-L1 expression on $\geq 50\%$ of tumor cells
- Cohort B3: will be conducted in Turkey, Georgia, Ukraine, and Taiwan. For Cohort B3, standard-of-care first-line treatment is defined as: standard local first-line chemotherapy. Patients must have demonstrated progressive disease after standard-of-care local first-line therapy, as defined by RECIST 1.1. PD-

L1 expression on tumor cells is determined centrally by a Sponsor-approved PD-L1 assay

- Cohort B4:

- Patients with recurrent, persistent or metastatic ovarian, primary peritoneal or fallopian tumor carcinoma of all histologic types, except mucinous adenocarcinoma and carcinosarcoma, with documented disease progression (disease not amenable to curative therapy) and a history of primary platinum-based chemotherapy
- Cohort B4 will be conducted in the US, Spain, UK, the Netherlands, Germany, Taiwan, Turkey, Georgia, and Ukraine. For Cohort B4, patients must have a history of primary platinum-based chemotherapy with a maximum of 3 prior cytotoxic regimens and with at least one regimen for recurrent disease containing a platinum or a taxane for those with 3 prior regimens; the last platinum-free interval must be \leq 12 months. Histologic confirmation of the original primary tumor is required via the pathology report. NOTE: Patients with mucinous or carcinosarcoma history are not eligible.
- Patients are allowed to have received up to 3 prior cytotoxic regimens for treatment of their epithelial ovarian, fallopian tube, or primary peritoneal cancer;
 - they must have had one prior platinum-based chemotherapeutic regimen for management of primary disease, which could include intra-peritoneal therapy, consolidation, biological/targeted (non-cytotoxic) agents or extended therapy (maintenance/consolidation) administered after surgical or non-surgical assessment;
 - patients are allowed to have received, but are not required to have received, one to 2 cytotoxic regimens for management of recurrent or persistent disease;
 - PARP inhibitors given for recurrent or progressive disease will be considered cytotoxic;
 - PARP inhibitors given as maintenance therapy in continuation with management of primary disease will not be considered as separate cytotoxic regimen;
 - if 2 cytotoxic regimens had been received for management of recurrent or persistent disease, one of these regimens would have had to contain either a platinum or a taxane agent

- Platinum-free interval (PFI) – patients must have progressed ≤ 12 months after completion of their last platinum-based chemotherapy; the date (PFI) should be calculated from the last administered dose of platinum therapy to documentation of progression
- Cohort B5:
 - Patients with head and neck squamous cell cancer with documented CPS ≥ 1 in the TME and as determined by an FDA-cleared* or any PD-L1 test approved for use by competent authority
 - Cohort B5 will be conducted in the US, Spain, UK, the Netherlands, and Taiwan. For Cohort B5, patients must have metastatic or unresectable, recurrent disease considered incurable by local therapies. Patients must qualify for in-label first-line, single-agent treatment with an approved anti-PD1 checkpoint inhibitor and as per investigator judgement would also be put on such treatment as part of standard-of-care, i.e., irrespective of clinical trial participation, at doses not exceeding those approved in local product labels.

** FDA-cleared tests include: PD-L1 IHC 22C3 (Dako; preferred assay), VENTANAPD-L1 (SP142; Ventana/Roche), and PD-L1 IHC 28-8 (Dako, VENTANA PD-L1 (SP263; Ventana/Roche), or any other companion /complementary diagnostic PD-L1 assay that may receive FDA approval during the conduct of this study.*

- Cohort B6:
 - Patients with TNBC according to current ASCO/CAP guidelines that is measurable according to RECIST1.1 criteria
 - Cohort B6 will be conducted in the US, Spain, UK, the Netherlands, and Taiwan. For Cohort B6, patients must have metastatic disease or locally advanced breast cancer (beyond curative management).
 - TNBC must be characterized as having $\leq 1\%$ cellular expression of ER and PR as determined by IHC and having HER2 expression of 0 to 2+ by IHC as per current ASCO/CAP Guidelines. If IHC 2+, a negative in situ hybridization test (preferably FISH; CISH or SISH acceptable) is required by local laboratory testing
 - Patients must have received at least one line of previous systemic therapy for advanced breast cancer (chemotherapy or targeted therapy allowed); however, patients must not have received more than 3 previous lines of cytotoxic chemotherapy (i.e., targeted agents not counting as previous line in this context)

- 20 patients in the cohort must have received prior therapy with an immune checkpoint inhibitor (i.e., an approved PD-1 or PD-L1 antibody), while the other 20 patients must not have received prior therapy with an immune checkpoint inhibitor (as per stratification)
- Cohort B8:
 - Cohort B8 will be conducted in the US, Spain, UK, the Netherlands, and Germany. Patients with metastatic, non-resectable colorectal cancer (mCRC) that is MSS or MSI low*, previously treated with all of the following:
 - fluoropyrimidine-, oxaliplatin-, and irinotecan-based chemotherapy,
 - and, if RAS wild-type, an anti-EGFR therapy, if eligible
 - Patients previously treated with an additional anti-VEGF biological therapy are also eligible
 - Patient agrees to paired biopsies and is judged by the investigator as safe for paired biopsies
 - Patients must have documented PD-L1 expression in the TME with PD-L1 expressed on at least 1% of tumor and/or immune cells, as detected by local testing with an FDA-cleared or any PD-L1 assay approved for use by local competent authority*.

*Eligibility determination can be done based on documented previous testing results. If no previous testing result is available eligibility determination will be done based on archival tissue or fresh biopsy taken during screening

3. Patients must provide tumor tissue (archival or fresh acquisition) at Screening for biomarker and PD evaluation. Archival tissue sample can be formalin-fixed paraffin-embedded (FFPE) tissue block(s) obtained within 5 years (for B cohorts: 2 years) before Screening (preferably within 12 months) or (at least 20) freshly sectioned unstained slides with tumor tissue present as per pathologist confirmation. Availability of tissue blocks is preferred over slides. Acceptable tissue sample include core needle punctured, resected or incisional biopsy, or surgical sample. (Note, fine needle aspirate (FNA) sample and tumor tissue from bone metastasis are not acceptable). Fresh biopsy should not be obtained from RECIST-defined target lesions if possible. Consult the Medical Monitor when no other lesions are suitable for biopsy, or in cases where archival tissue was obtained outside the above-specified timeframes, as exceptions may be approved on a case-by-case basis.
4. **Cohort B8:** For biomarker and PD evaluation, MSS or MSI low mCRC patients enrolled must mandatorily provide freshly acquired tumor tissue (primary tumor or metastases) at Screening and – whenever considered clinically feasible as per investigator judgement – at least once

while on treatment. Acceptable tissue sample include core needle punctured, resected or incisional biopsy, or surgical sample. (Note, FNA sample and tumor tissue from bone metastasis are not acceptable). Fresh biopsy should not be obtained from RECIST-defined target lesions if possible. Consult the Medical Monitor when no other lesions are suitable for biopsy. At least 3 biopsy cores, but preferably more if considered safe by the radiologist, shall be taken at each biopsy event and touch preparation as per site standard approach shall be applied to ensure specimen adequacy (i.e., confirm tumor content). In addition to these fresh biopsies, for patients for whom there is archival primary tumor tissue available, this archival tissue, as per inclusion criterion #3 requirements, shall also be provided for biomarker analysis.

5. **Part A:** Patients with liver metastases may be enrolled provided that less than 50% of the liver is involved according to the judgement of the Investigator.
6. ECOG performance status 0 or 1.
7. Life expectancy \geq 12 weeks.
8. Must have at least 1 measurable lesion per RECIST 1.1 that is progressing or new since last anti-tumor therapy. The measurable lesion(s) can be inside the field of prior radiotherapy (RT) provided that the lesion has documented progression post RT as per RECIST 1.1.
9. **Part A & A-2:** Prior chemotherapy or systemic radiotherapy (for immunotherapy see exclusion criteria) must have been completed at least 4 weeks prior to the administration of the first dose of study drug, and patient has recovered to Common Terminology Criteria for Adverse Events (CTCAE) V5.0 Grade 1 or better from all AEs associated with prior therapy or surgery (however, sensory neuropathy, alopecia and endocrine disorder treated with hormone replacement \leq Grade 2 is acceptable).

Part B: *For Cohort B1, B2, B6 (subgroup with required previous checkpoint inhibitor therapy) and B7:* Last dose of therapy with anti-PD-1 monotherapy must have been received at least 2 weeks prior to the administration of the first dose of the study drug. *All Part B Cohorts (while not applicable to Cohort B5):* Prior chemotherapy must have been completed at least 4 weeks prior to the administration of the first dose of study drug. Exceptions: Hormone (e.g., thyroid hormone) replacement therapy.

10. Prior treated brain or meningeal metastases must be without magnetic resonance imaging (MRI) evidence of progression for at least 8 weeks and off immunosuppressive doses of systemic steroids (>10 mg/day prednisone or equivalent) for at least 2 weeks prior to the administration of the first dose of study drug; patients must be without neurologic dysfunction that would confound the evaluation of neurologic and other AEs (patients with a history of carcinomatous meningitis are not eligible).

11. **Part A & A-2:** Breast cancer patients who are receiving adjuvant hormonal therapy are eligible.
12. Prior systemic RT must have been completed at least 4 weeks prior to the administration of the first dose of study drug. Prior focal radiotherapy must have been completed at least 2 weeks before first study drug administration. No radiopharmaceuticals (strontium, samarium) must have been used within 8 weeks prior to the administration of the first dose of study drug.
13. Immunosuppressive medication including immunosuppressive doses of systemic steroids or absorbed topical steroids (doses >10 mg/day prednisone or equivalent) must be discontinued at least 2 weeks prior to the administration of the first dose of study drug.
14. Prior major surgery that required general anesthesia must be completed at least 2 weeks prior to the administration of the first dose of study drug; minor surgical procedures (such as e.g. laparoscopy, endoscopy, port insertion etc.) conducted under general anesthesia or surgery requiring regional/epidural anesthesia must be completed at least 72 hours prior to the administration of the first dose of study drug and patients should be recovered. Cutaneous biopsies with only local anesthesia should be completed at least 1 hour prior to the administration of the first dose of study drug.
15. Screening laboratory values must meet the following criteria:
 - Hematological:
 - White blood cell (WBC) $\geq 2.0 \times 10^9/L$
 - Absolute neutrophil count (ANC) $\geq 1.5 \times 10^9/L$
 - Lymphocyte count $\geq 0.5 \times 10^9/L$
 - Platelets $\geq 100 \times 10^9/L$
 - Hemoglobin ≥ 9 g/dL
 - Renal: serum creatinine $\leq 1.5 \times$ upper limit of normal (ULN) or calculated using the Cockcroft-Gault formula or measured creatinine clearance >50 mL/min.

Female creatinine clearance

$$= \frac{(140 - \text{age in years}) \times \text{weight (kg)} \times 0.85}{72 \times \text{serum creatinine in mg/dL}}$$

Male creatinine clearance

$$= \frac{(140 - \text{age in years}) \times \text{weight (kg)} \times 1.00}{72 \times \text{serum creatinine in mg/dL}}$$

- Hepatic:

- Total bilirubin $\leq 1.5 \times \text{ULN}$ (except patients with Gilbert's syndrome, who must have total bilirubin $\leq 3.0 \times \text{ULN}$)
- AST and ALT $\leq 2.0 \times \text{ULN}$
- **Cohort B8:**
 - Serum albumin $\geq 30 \text{ g/L}$ (3.0 g/dL)
 - Lactate dehydrogenase $\leq 2.5 \times \text{ULN}$
- Coagulation:
 - International Normalized Ratio or Prothrombin time (PT) $\leq 1.5 \times \text{ULN}$ unless patient is receiving anticoagulant therapy as long as PT or Partial Thromboplastin Time (PTT) is within therapeutic range of intended use of anticoagulants based on the institutional standard-of-care
 - Activated Partial Thromboplastin Time $\leq 1.5 \times \text{ULN}$ unless patient is receiving anticoagulant therapy as long as PT or PTT is within therapeutic range of intended use of anticoagulants based on the institutional standard-of-care
- Thyroid stimulating hormone (TSH) is required to be within normal limits at baseline; however, if TSH is not within normal limits at baseline, the patient may still be eligible if total triiodothyronine (T3) or free T3 and free thyroxine (T4) are within the normal limits.

16. Female patients must have a negative serum pregnancy test within 72 hours prior to the administration of the first dose of study drug if of child-bearing potential or be of non-child-bearing potential. In case of a positive serum pregnancy test, the site is allowed to apply standard site procedures to rule out false positive test results; enrollment of the patient may be considered only in case of false positivity of the serum pregnancy test has been confirmed. A urine pregnancy test is to be done prior to dosing at all other time points and must be negative prior to the administration of the first dose of study drug.

If the urine test is positive or cannot be confirmed as negative, a serum pregnancy test will be required. The serum pregnancy test must be negative for the patient to be eligible for continued treatment with the study medication. Non-child-bearing potential is defined as (by other than medical reasons):

- ≥ 45 years of age with continuous amenorrhea for >2 years and a follicle stimulating hormone (FSH) of $>40 \text{ IU/L}$ upon pre-study (Screening) evaluation.
- Women who were surgically sterilized, i.e., had a hysterectomy and bilateral oophorectomy, or have a documented permanent female sterilization procedure including tubal ligation. Documented hysterectomy or oophorectomy must be confirmed with medical records of the actual procedure or confirmed by an ultrasound. Tubal ligation

must be confirmed with medical records of the actual procedure otherwise the patient must be willing to utilize a reliable form of contraception (either medication – oral, implant or injection – or a barrier method). In general, the decision for appropriate methods to prevent pregnancy should be determined by discussions between the Investigator and the study patient. A FSH level can be used to confirm post-menopausal status in amenorrheic patients not on hormonal therapy.

- Women of child-bearing potential (WOCBP) must agree to use a highly effective method of contraception (i.e. pregnancy rate of less than 1% per year) during the study Treatment Period and for 180 days following the last dose of study drug.

17. Men who have female partners of child-bearing potential must agree to the use of contraception during the study Treatment Period and for at least 180 days after the last dose of study drug (see [Appendix V, Section 18.5](#)).
18. No active bleeding.
19. Able to understand and give written informed consent and comply with study procedures.
20. **Part A-2:** Documented minimal PD-L1 expression on at least 1% of tumor and/or immune cells in the TME, as detected by a local testing with an FDA-cleared or any PD-L1 assay approved for use by local competent authority.
21. **Part B:** Must have received complete Covid-19 vaccination within the timeframe considered to provide protection at the time of study enrollment according to current local guidelines, or must have a negative Covid-19 test polymerase chain reaction (PCR) test result.

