18.5 Appendix V: Women of Child-Bearing Potential Definitions and Methods of Contraception

Definitions

Woman of Child-bearing Potential (WOCBP): A woman is considered fertile following menarche and until becoming post-menopausal unless permanently sterile. Permanent sterilization methods include hysterectomy, bilateral salpingectomy, and bilateral oophorectomy.

Women in the following categories are not considered WOCBP:

- Premenarchal
- Premenopausal female with 1 of the following:
 1. Documented hysterectomy
 2. Documented bilateral salpingectomy
 3. Documented bilateral oophorectomy

Note: Documentation can come from the site personnel's review of the participant's medical records, medical examination, or medical history interview.

Post-menopausal female: A post-menopausal state is defined as 12 months of amenorrhea in a woman over age 45 years in the absence of other biological or physiological causes. In addition, females under the age of 55 years must have a serum FSH level >40 mIU/mL to confirm menopause.

Contraception Guidance for Female Participants of Child-Bearing Potential

One of the highly effective methods of contraception listed below is required during study duration and until the end of relevant systemic exposure, defined as 180 days after the end of study treatment (local laws and regulations may require use of alternative and/or additional contraception methods).

Highly Effective Contraceptive Methods That Are User Dependent
Failure rate of <1% per year when used consistently and correctly.^a

• Combined (estrogen- and progestogen-containing) hormonal contraception associated with inhibition of ovulation^b
– oral– intravaginal– transdermal• Progestogen-only hormonal contraception associated with inhibition of ovulation^b
– oral– injectable
Highly Effective Methods That Are User Independent

• Implantable progestogen-only hormonal contraception associated with inhibition of ovulation^b• Hormonal methods of contraception including oral contraceptive pills containing a combination of estrogen and progesterone, vaginal ring, injectables, implants and intrauterine hormone-releasing system (IUS)^c• Intrauterine device (IUD)^c• Bilateral tubal occlusion

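### Criterion 16 and Appendix V define non-child-bearing potential differently, and nothing says which one governs pregnancy testing and contraception after entry

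*Protocol*

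**What the plan says.** Criterion 16 (Protocol Section 7.2.1) gives two routes to non-child-bearing potential.

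- **Menopause:** at least "45 years of age with continuous amenorrhea for >2 years and a follicle stimulating hormone" level above 40 IU/L at Screening. No age is given above which FSH is waived.
- **Surgery:** hysterectomy and bilateral oophorectomy, "or have a documented permanent female sterilization procedure including tubal ligation". Hysterectomy or oophorectomy must be confirmed by procedure records or ultrasound. Ligation must be confirmed by procedure records; "otherwise the patient must be willing to utilize a reliable form of contraception", and a barrier method is among the options.

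A further bullet of criterion 16 requires WOCBP to use a highly effective method, with a pregnancy rate below 1% per year, during treatment and for 180 days after the last dose.

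Appendix V (Section 18.5) has its own definition. Menopause there is "defined as 12 months of amenorrhea in a woman over age 45 years in the absence of other biological or physiological causes", and "females under the age of 55 years must have a serum FSH level >40 mIU/mL to confirm menopause". On surgery it says: "Permanent sterilization methods include hysterectomy, bilateral salpingectomy, and bilateral oophorectomy". Any one of these three, documented, is enough, and a medical history interview is an accepted source. "Bilateral tubal occlusion" appears in its list of highly effective contraceptive methods. Condom, diaphragm, cap and sponge are in its unacceptable list.

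Footnote o of Tables 7-1 and 7-2 limits urine pregnancy tests after Screening to WOCBP. It refers the FSH check to inclusion criterion 15.

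**The concern.** Footnote o makes the definition operational: a woman's status decides whether she is tested on treatment. Appendix V is operational too. It requires a listed method, and it ties WOCBP to the pregnancy tests of Section 7.1.6. Criterion 16 does not cite Appendix V, although criterion 17, for men, does. No section states an order of precedence once a patient is enrolled.

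The drug is a first-in-human immune agonist with a 180-day contraception requirement after the last dose. At stake is consistent handling of pregnancy risk across sites. A woman could be tested and required to use contraception under one section, and be exempt under the other.

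**Working it through.** There is no planned figure to reproduce. The check sets the two texts side by side and applies each to example patients.

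| Element | Criterion 16 | Appendix V |
|---|---|---|
| Amenorrhea | more than 2 years | 12 months |
| FSH above 40 | always | only under age 55 |
| Documented tubal ligation | non-child-bearing | contraception for WOCBP |
| Hysterectomy, bilateral oophorectomy | joined by *and* | either alone is enough |
| Proof of hysterectomy or oophorectomy | records or ultrasound | interview accepted |
| Barrier method, ligation unrecorded | accepted | listed as unacceptable |

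Three things are not material differences.

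- The FSH cut-off is the same, since 40 IU/L = 40 mIU/mL.
- Both texts exclude amenorrhea from another cause. Criterion 16 opens its definition with "Non-child-bearing potential is defined as (by other than medical reasons", and Appendix V has the equivalent clause quoted above.
- The lower age limit (45 or older against over 45) differs only trivially.

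**Number of tests (Table 7-1, two-week dosing).** Day 1 of odd-numbered cycles within Cycles 1-8 means Cycles 1, 3, 5 and 7 (Days 1, 57, 113, 169), which is 4 urine tests. The follow-up column carries no FU1-only limit for this row, so FU1 to FU3 add up to 3. The total after Screening is 4 + 3 = up to 7. The Screening serum test is left out: footnote o does not limit it to WOCBP, although criterion 16 does.

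**Example patients**

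1. *Age 50, 18 months of amenorrhea with no other cause, FSH 45 IU/L.* Criterion 16: 18 < 24 months, so she is of child-bearing potential, with 4 on-treatment tests, up to 3 at follow-up, and highly effective contraception through treatment plus 180 days. Appendix V: 18 ≥ 12 months and 45 > 40, so she is post-menopausal, with no such tests and no contraception requirement.
2. *Age 60, 10 years of amenorrhea, no FSH result.* Criterion 16 is not met until FSH is shown to exceed 40. Appendix V is met. The FSH test already provided for at Screening can settle this case.
3. *Age 38, documented ligation.* Criterion 16: no on-treatment urine tests. Appendix V: 4, plus up to 3 at follow-up. Contraception is satisfied either way, because Appendix V counts tubal occlusion as highly effective.
4. *Age 38, ligation without records.* Criterion 16's fallback allows a barrier method. Its WOCBP bullet requires a pregnancy rate below 1% per year, and Appendix V rejects barrier methods.
5. *Age 42, hysterectomy alone.* Appendix V: not WOCBP. Criterion 16 is ambiguous, because it joins hysterectomy to bilateral oophorectomy.

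Neither text is stricter throughout. Criterion 16 is stricter on menopause and proof; Appendix V is stricter on ligation and barrier methods.

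**The case against.** The strongest reply is that criterion 16 governs. Section 7.2.1 admits patients only if every criterion applies, and Section 7.2 forbids waivers. Footnote o also names an inclusion criterion as the source for non-child-bearing potential. Its number 15 looks like a renumbering slip, since footnote n likewise cites criterion 14 for the coagulation values that sit in criterion 15.

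Much of this stands. A reader might infer that a site could use Appendix V to bypass criterion 16 at entry; the documents do not support that. The footnote also leans toward criterion 16 for menopause, though its sentence concerns the FSH check and does not settle ligation status, contraceptive method or proof. What remains open is the rule after entry.

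A reader might also infer that criterion 16 simply lets a woman with unrecorded ligation rely on condoms. It does not. She has not shown a documented sterilisation, so the natural reading is that she is WOCBP and the below-1% bullet applies. The fallback clause is thus at odds with its own criterion as well as with Appendix V, which is a reason to delete it.

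Finally, exclusion 24 and discontinuation for pregnancy (Section 7.2.9) apply under either text. They protect patients once a pregnancy or an intention to conceive is known, but they do not decide who is tested or which method is acceptable.

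**Conclusion.** The inconsistency is real and minor. On-treatment urine testing can differ by 4 tests over Cycles 1-8, plus up to 3 at follow-up, for the same woman. The contraception required can differ in the menopause and unrecorded-ligation cases. The test count assumes the two-week schedule, eight cycles completed and all three follow-up visits attended.

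Two larger claims should not be drawn. A contrast of no tests against 8 would add the Screening serum test, which is not on treatment and which footnote o does not restrict to WOCBP. And for documented ligation, the case in the lead quotation, contraception does not differ at all.

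Reach was small. SAP Section 6 reports 5 + 5 + 10 = 20 patients in Part B and 5 in Part A-2, and neither document gives the split by sex. No endpoint, analysis set or statistical result is affected.

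**What to change.** - Delete the barrier-method fallback from criterion 16.
- Keep a single definition of non-child-bearing potential and a single list of acceptable methods, in whichever section the sponsor prefers, and have the other section refer to it.
- In that definition, state one amenorrhea/FSH rule, one status for tubal ligation and one standard of proof. These are the sponsor's choices. Hysterectomy alone or bilateral oophorectomy alone should still count as non-child-bearing. For that reason, taking the stricter half of each pair mechanically is not advised: it could class a woman with hysterectomy alone as of child-bearing potential.
- Correct footnote o of Tables 7-1 and 7-2 from criterion 15 to criterion 16.

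The cost is wording in criterion 16, Appendix V and two footnotes. If ligation is treated as contraception, a woman with documented ligation gains 4 urine tests over Cycles 1-8 and up to 3 at follow-up, plus the Screening serum test where it would otherwise be omitted. All fall at visits already scheduled. No analysis changes. The SAP records early closure of the trial, so if the protocol is not amended again, the correction belongs in any successor protocol that reuses this text.
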